Mount Sinai Hospital has developed a Rapid Response Team (RRT) system designed to give general floor care providers additional support for patients who may be requiring a higher level of care. This system enables both nurses and physicians to notify the RRT and have a critical care team evaluate the patients. During the period of 03/01/2018 to 09/17/2018, Mount Sinai Hospital floor units on 10W and 10E units made 357 rapid response team (RRT) calls with only 58 leading to an actual increase in the level of care (true positive rate ~ 16%). Similarly, the Electronic Health Record (EHR) generated 839 sepsis Best Practice Alerts (BPAs) yet only five led to escalations in care (true positive rate ~ 0.5%). The results above would imply that over 168 evaluations need to be made to identify a single case where the patient required an escalation in care. The goal of ReSCUE-ME is to evaluate prospective model performance and identify the best spot which we can incorporate MEWS++ into RRT and Primary providers workflow. The primary endpoint is rate of escalation of care on 10W and 10E during the study period.

Background

In a prior study, our group has demonstrated that a machine learning model (MEWS++) significantly outperformed a standard, manually calculated MEWS score on a large retrospective cohort of hospitalized patients. To develop this model, we used a data set (Approved by: IRB-18-00581) of 96,645 patients with 157,984 hospital encounters and 244,343 bed movements. We found that MEWS++ was superior to the standard MEWS model with a sensitivity of 81.6% vs. 44.6%, specificity of 75.5% vs. 64.5%, and area under the receiver operating curve of 0.85 vs. 0.71. Encouraged by this prior result, we are seeking to evaluate our model in a prospective study.

A silent pilot of the ReSCUE-ME alerts has been running on 10E and 10W since Feb 2019. We have been continuously monitoring the alert performance via a real-time web-based dashboard. The results are summarized below:

- Median # of alerts to primary team, per floor, per day: 8
- Median # of alerts to RRT, per floor, per day: 4
- Sensitivity 0.76, Specificity 0.68, AUC 0.77
- Accuracy 0.69, Precision 0.3, F1 Score 0.43

This performance compares very favorably to the performance seen in the retrospective historical cohort used to develop the MEWS++ model:

- Sensitivity 0.82, Specificity 0.76, AUC 0.85
- Accuracy 0.76, Precision 0.12, F1 Score 0.19"

Primary and Secondary Study Endpoints

Primary Endpoints:

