6. Subjects - Enrollment

Site Name The Mount Sinai Hospital
Subjects To Be Enrolled
18680
Total Number of Subjects to be Enrolled Across All Listed Sites Above (Auto Populated) 18680

7. Subjects - Setting and Resources

Setting of Human Research Other

Specify Other Setting of Human Research

Hospital Units on 10W, 10E, 9W, 9E.

Total Number of Subjects Needed 18680

To Complete Study

Feasibility of Meeting Recruitment Goals

Our initial observation shows the rate of escalation ~ 10% for the selected units (10W and 10E). The estimated sample size is ~ 934 escalations of care which we expect to observe by including ~9340 bed movements. The estimated bed movements per day in the selected units is ~ 10 which makes the expected pilot days ~ 934 days (~ 2.5 yrs.). We anticipate an equal number of escalations for 9W and 9E, which will not receive any MEWS++ alerts.#

Facilities To Be Used for Conducting Research

Hospital Units on 9W, 9E, 10W, 10E

Multi-Center Study No

Community-Based Participant Research Study No

PI must attest to the following.

**** Process is adequately described to ensure that all persons assisting with the trial are adequately informed about the protocol, the investigational product(s), and their trial-related duties and functions.***

8. Subjects - Populations

Inclusion Criteria

All patients age 18 or greater who were admitted to a general care unit on 9W, 9E, 10W, 10E.

Exclusion Criteria

Any admitted patient who has a "Do Not Resuscitate (DNR)" and/or a "Do Not Intubate (DNI)" order in the EHR, any patient made "level of care" by RRT as documented in REDCap.

Enrollment Restrictions Based No

**Upon Gender, Pregnancy,
Childbearing Potential, or Race**

Age Range(s) 18 to 64 Years, 65 Years and Over

Targeted Population(s) Adults - Patients

Other Aspects that Could Increase Subjects Vulnerability

Prisoners and non-laboring pregnant women will be included if they are admitted to 10E/W or 9E/W. This will be rare but possible. Incapacitated patients will be provided the study information sheet within their paper chart and included unless their health care proxy/legally authorized representative chooses to opt them out of the study. If they were to regain consciousness and capacity, then they would have the ability to withdraw from the study."

Safeguards to protect Subjects rights and welfare

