Description of the study protocol will be given to participants upon admission to the floor. We will instruct the Business Associate and nursing team members to specifically call to attention to the provided information sheet when a patient is admitted to the unit. We will also post prominent printed notices describing the study throughout the unit (e.g. on the walls near the nursing desk, on any bulletin boards designed for patient communication, etc). Furthermore, if a patient does trigger an alert, the RRT staff will be instructed to notify the patient of the information sheet. Finally, upon discharge, the information sheet would be provided again to the patient as part of their check-out. As such, there exists at least 3 touch points for the patient to discuss the study with a care provider.

How Participants Will Be Screened

Automated screening by the software that generates alerts.

10. Subjects - Risk and Benefits

Risks to Subjects

The MEWS++ alerts will serve to notify the care team of a potential deterioration in a patient's clinical condition. What the provider may choose to do with the MEWS++ alert is left completely to their discretion and we do not propose any determination of care by the MEWS++ alert. As a result, there will be no alteration in the standard of care. All therapeutic interventions will be at the discretion of the care providers and the expected risk of monitoring for select individuals within the interventional cohort should be minimal. The potential risk of breach of confidentiality or loss of protected healthcare information (PHI), will be unlikely as all data will be password protected and any patient identifiers will be encrypted; furthermore, all data gathering will be done on Mount Sinai internal network computers and devices.#

We do not change any workflow for the primary team and RRT. We just increase awareness in the clinicians' mind that a patient may be in danger of deterioration. The primary intervention by the Primary team is simply to increase the frequency of vitalsigns measurement. This will not be associated with any risk or patient safety concerns. We will not remove any of current notifications being received by RRT we will just add one more notification to the current workflow.

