Inducing a false sense of security is perhaps unavoidable with the introduction of any new monitoring modality. During our education sessions with providers, it will be stressed that MEWS++ is an investigational alert and it should not override clinical judgement. We will have two further mechanisms for soliciting clinician feedback and ensuring a false sense of security is not imbued in the staff. First, we will be in close communication with nursing and RRT leadership throughout the pilot, via check-in meetings initially weekly, and then monthly or as needed throughout the study. Second, the RRT team logs details of every RRT visit to a REDCap database. These data are automatically integrated into our analysis pipeline. We match alerts to RRT calls as part of our performance monitoring. If a deterioration occurs that is missed by our algorithm but seen by RRT, will be able to analyze and understand what factors may have contributed to the miss, and if alert fatigue or a false sense of security contributed to the miss.

Description of Procedures Taken to Lessen the Probability or Magnitude of Risks

No additional data will be gathered beyond that of the standard of care for patients, thus limiting risks of the additional information. The research personnel table lists all personnel who may obtain viewing privileges to the collected data.

Provisions for Research Related Harm / Injury

There is no risk of research related to harm or injury as no therapeutic intervention is made based on the results from this study's evaluation. All participant will receive standard of care interventions.

Expected Direct Benefit to Subjects

As a direct benefit from enrolling in this study, we expect the subjects will be more closely monitored for deterioration in clinical condition and will receive more immediate escalation in care when compared to both historical and matched control subjects.

Benefit to Society

We hope that the proposed technology will prove to have a highly sensitive and specificity for predicting individuals who are at risk of clinical deterioration and may require a higher/more intensive level of care. If this does prove to be true, this would be a significant advance to the field of medicine. It would help to reduce death within an inpatient hospital setting.

Provisions to Protect the Privacy Interests of Subjects

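### The RRT 'level of care' exclusion has no time limit in the visible text; if it defines the analysis set, it selects patients on a post-admission event that one-arm alerts could influence

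*Combined protocol and SAP*

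**What the plan says.** Section 8 (Subjects - Populations) includes adults admitted to 9W, 9E, 10W or 10E and excludes "any patient made 'level of care' by RRT as documented in REDCap". The same sentence excludes patients with a DNR or DNI order. Neither rule carries a time point.

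On where the status comes from, Section 10 (Risk and Benefits) states that "the RRT team logs details of every RRT visit to a REDCap database".

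On the difference between arms, Section 7 describes the control units as "9W and 9E, which will not receive any MEWS++ alerts". On 10E/10W, Section 11 (Procedures - Narrative) has a sufficiently high MEWS++ score notify the RRT directly. Section 10 presents this as an addition, "we will just add one more notification to the current workflow", and leaves the response to the clinicians.

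On how exclusions operate, the screening entry in Section 9 reads "Automated screening by the software that generates alerts", and Section 11 (source records) has scores generated for patients who are neither excluded nor withdrawn.

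The Final Statistical Analysis Plan takes each patient's first hospitalization, fixes the arm at admission, and applies stabilized inverse probability of treatment weights (IPTW) for differences in baseline characteristics. It does not mention the Section 8 exclusions.

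**The concern.** An exclusion is safe for a comparison between arms when it is settled before the intervention can act. This one is an RRT decision that can be made at any point in the stay. In one arm the study adds a route by which the RRT is called to a patient's attention. If alerts lead to more (or different) patients receiving the status on 10E/10W, and those patients then leave the analysis set, the two arms no longer hold comparable patients, even if they did at admission.

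Fixing the arm at admission does not help, because the loss comes afterwards. Baseline IPTW does not help either, because the selecting event is not a baseline variable. The primary composite in Section 3 includes RRT-initiated therapy, so the exclusion also sits close to the endpoint. The visible text neither gives nor plans exclusion counts by arm, so a reader could not tell whether any of this happened.

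**Working it through.** **1. Is there a time rule elsewhere?** Sections 9 and 11 describe what happens to the data of patients who withdraw. Neither covers a patient who meets an exclusion after entry. Section 9 places screening in the alert software and Section 11 links exclusion to scoring, which fits an exclusion that only switches scoring off. Section 8 lists the rule as a study exclusion criterion, which fits removal from the study. The final SAP does not choose between them.

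**2. The plan's own figures.**
- Section 3 reports "357 rapid response team (RRT) calls with only 58 leading to an actual increase in the level of care": 58/357 = 16.2%, matching the stated ~16%.
- The power section in Section 19 states a 5% margin without a scale. With 10% in both arms, 95% power and a one-sided 2.5% level, n = 2 × 0.10 × 0.90 × (1.960 + 1.645)² / 0.05² = 936, against 934 stated. Reading the margin as 5 absolute points therefore fits.
- The effect implied by the same section is 10% escalation × 50% identified × 20% prevented = 0.10 × 0.50 × 0.20 = 0.01, or 1 point.

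**3. Size of a possible shift.** Let p be the true escalation rate, x the share dropped, and r the escalation risk of those dropped. The observed rate is (p − x·r)/(1 − x). Take p = 0.10 in both arms (no alert effect) and x = 1% in control. The values of x are assumptions, as are those of r except 16%. Entries are MEWS++ minus control, in percentage points:

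| Dropped, MEWS++ vs control | r = 0% | 10% | 16% | 30% | 50% |
|---|---|---|---|---|---|
| 1.5% vs 1% | +0.05 | 0 | -0.03 | -0.10 | -0.21 |
| 2% vs 1% | +0.10 | 0 | -0.06 | -0.21 | -0.41 |
| 3% vs 1% | +0.21 | 0 | -0.13 | -0.42 | -0.83 |

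Example: 3% vs 1% at r = 50% gives (0.10 − 0.015)/0.97 = 8.76% against (0.10 − 0.005)/0.99 = 9.60%, a difference of -0.83 before rounding. With equal shares and equal risks the difference is zero.

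**4. Scale.** Against 5 points, 0.13 is 2.6% (0.13/5) and 0.83 is 17% (0.83/5). With 9,340 per arm the standard error of the difference is √(2 × 0.10 × 0.90/9340) = 0.44 points. A two-sided 5% superiority test with no true effect would then reject about 6% of the time at -0.13, 16% at -0.41 and 50% at -0.83.

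**5. What the assumed shares require.**
- Calls: 03/01/2018 to 09/17/2018 is 201 days, so 357/201 = 1.78 calls per day on 10E/10W. Section 7 says "The estimated bed movements per day in the selected units is ~ 10", so 1.78/10 = 0.178 calls per bed movement. Dropping 1% needs 0.01/0.178 = 5.6% of calls to end in the status.
- Alerts, silent pilot (Section 3): "Median # of alerts to RRT, per floor, per day: 4". For the two units that is 4 to 8 per day, depending on what a floor means, or 0.4 to 0.8 per bed movement. Each extra point dropped needs 0.01/0.8 = 1.25% to 0.01/0.4 = 2.5% of alerts to end in the status.
- Alerts, Section 10: 5 per 12 hours per floor is 10 to 20 per day, or 1 to 2 per bed movement, so 0.5% to 1% of alerts.

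These treat medians as means and each call or alert as a separate bed movement; repeats raise the shares needed. They show what the assumptions demand, not what occurred.

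**The case against.** The harmless reading is a serious one. Sections 9 and 11 attach exclusion to the alert software, and the final SAP describes first hospitalizations without naming any later removal. If exclusion only stops scoring, there is no selection bias. That stands as a possibility, but the SAP does not state it.

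Several appendices (notification process, data elements, opt-out program) are not in view and may define or time the status. So the statement that there is no time limit covers the visible text only.

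The size is mostly assumption. The one risk taken from the documents gives at most -0.13 points, and it is escalation per RRT call, not risk among patients given the status. The model also gives dropped patients the same risk in both arms and counts bed movements, whereas the final SAP analyses patients. All of this stands. Section 11 moreover states an equivalence aim, for which shifts of this size matter little.

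A reader might infer more: that alerts brought the RRT to more patients, that those patients were dropped, and that the comparison is biased. The documents do not support this. The alert is a notification with a discretionary response, no counts by arm are given, and the status is undefined (Section 3 uses the phrase for escalation itself). Nor does the remark in the Summary of Changes that alerts were capped in both arms settle the matter: it concerns alerts generated, while Sections 7 and 11 say none go to 9E/9W.

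For DNR/DNI orders the case is weaker still, since nothing links alerts to those orders.

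**Conclusion.** The point holds conditionally. The visible text leaves open both the timing of the exclusion and whether it defines the analysis set. If it does so as worded, it can bias the comparison in a way the planned weighting cannot repair. Whether that happened, in which direction and by how much cannot be determined from the documents.

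On the illustrated assumptions (10% true rate in both arms, differential loss of 0.5 to 2 points), the shift is -0.03 to -0.13 points at the 16% proxy risk and at most -0.83 points at 50%. It turns positive if the dropped patients have below-average risk. Mortality and the RRT-therapy part of the composite are not covered by this calculation. Under the equivalence aim or a 5-point margin the issue is minor. It matters mainly if the final SAP's ratio estimates are read as evidence of superiority, because the planned effect derived above is only about 1 point. It should be corrected, and confidence is medium.

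**What to change.** In the SAP, state whether the Section 8 exclusions define the analysis set, and define 'level of care'. For the analysis set:

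- apply that exclusion only where the status was recorded at or before admission to the index unit, using REDCap visit times;
- keep patients designated later in their admission arm, and say how their later outcomes are counted;
- report later designations by arm;
- run the exclusion as worded in Section 8 as a sensitivity analysis;
- for consistency, use the same time rule for DNR/DNI orders, from EHR order times.

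First check that these times are complete in both arms. The Summary of Changes calls data from a separate RRT call tracking system unusable and does not say whether that is the REDCap log. One sentence on whether alerts were generated but not sent on 9E/9W would also help.

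The cost is SAP wording, a time filter, a completeness check and one extra analysis. The downside is that some later-designated patients, number unknown, stay in and may dilute the target population. If REDCap times are incomplete, the 'level of care' part can only be reported as a limitation.

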All key personnel have been HIPAA trained. All data will be encrypted and stored on secure servers within the hospital data center, with access restricted based on involvement in the project. Patients will also be offered multiple methods of withdrawing participation consent from the study, which includes by phone, email, website, and nursing care.

9. Subjects - Participation

Duration of an Individual Subjects Participation in the Study

During the entirety of their care on 9W, 9E, 10W, 10E

Duration Anticipated to Enroll All Study Subjects

We anticipate, given the current volume of bed movements, that it will take 30 months to complete enrollment.

Estimated Date for the Investigators Within 3-5 years
to Complete This Study

Procedures for Subjects to Request Withdrawal

Subjects may also withdraw from permission for the use and disclosure of any of your protected information for research and can do so by contacting the unit business associate "BA", by email to [contact] or by calling to [contact] with the information specified in "Waiver Information Sheet" (Appendix 1).

Procedures for Investigator to Withdraw Subjects

The Principal Investigator may stop subject involvement in this research study at any time without subject consent. This may be because the research study is being stopped, the instructions of the study team have not been followed, the investigator believes it is in their best interest, or for any other reason.

"Not participate" or "withdraw" means the alerting will be suppressed/turned off for the patient, their data will not be collected, and no alerts will be sent. Any data or alerts prior to withdrawal will be retained. This information has been added to the consent.

Participants Will Be Recruited Yes

Recruitment Method(s) Clinical Practice

How Participants Will Be Identified

All patients admitted to 10E, 10W, 9E, and 9W

Who Will Initially Approach Potential Participants Clinic Personnel

How Research Will Be Introduced to Participants

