One possible risk is alert fatigue. The primary cause of alert fatigue for the RRT team is currently the "Sepsis BPA" generated by Epic, not clinician generated alerts or the alerts that will be generated by this study. The alerting protocol attached to the application was carefully designed to minimize the number of additional alerts. Based on our modeling we anticipate 5 additional alerts to RRT per additional 12-hour shift. This is confirmed by the silent pilot. This was extensively discussed with both nursing and RRT leadership who agreed that the burden of this additional alerting is tolerable. The Sepsis BPA's generate far more alert fatigue. They are being modified to fire less frequently, as part of a non-IRB approved PI/QI changes being made directly by the CMO's office and Epic implementation team, independent of this protocol.

In order to minimize alert fatigue from our alerts, we will be continuously trending the alert burden of the study via the web dashboard and other custom analytic tools. In addition, care provider participants will be polled for their degree of alert fatigue. A review committee will be formed to assess the need to adjust the degree of alerting.

Currently the RRT team and floor nurses are overburdened by Sepsis BPA alerts. Our alerts are more sensitive and more specific and are carefully calibrated to fire less often based on both the retrospective data used to develop the alert and our silent pilot. c. Since the number of alerts is fairly low (5 alerts per 12 hours per floor) and the refractory period can be adjusted automatically based on the clinicians' judgment (see below), we don't believe we will encourage "over testing".

It should be noted that over testing is often a result of inability to ignore results of alerts without perceived medicolegal ramification. By the very fact that our alert is investigational, it would not produce similar concerns.

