By only allowing only members of the investigational team to access PHI we protect subjects' privacy. All study personnel has completed HIPAA training, which ensures the utmost care is used to handle PHI.

Economic Impact on Subjects

There is no economic burden on the patient.

11. Procedures - Narrative

Description of the Study Design

Patients admitted to 10W and 10E meeting the inclusion and exclusion criteria will undergo a modified RRT evaluation protocol as detailed in Appendix 4: Process Flow. In brief, the patient will be evaluated based on our retrospectively validated machine learning algorithm (MEWS++) designed to improve identification of patients who may need care escalation. Patients on 9W and 9E will be followed but no alerts, interventions or changes from standard of care will be pursued. The study is designed to evaluate the equivalence in the proportion of escalations between the standard of care RRT protocol and our proposed ReSCUE-ME protocol. Patients admitted to 9W and 9E will not undergo any additional monitoring and thus will serve as controls.

Further details of the alerting system are listed below.

- a. Notifications can be suppressed or re-enabled on a per-patient basis. This is a core feature as it is needed to fulfill the opt-out process that we documented in our application's appendices.
- b. Currently there are several automated alerts sent to Vocera. These include ventilator and telemetry alarms, e.g. an alarm if the ECG monitor detects asystole. There is also a simple rules-based Epic BPA for hyperkalemia that sends an alert to the Vocera if a patient's potassium level is high. There is an administrative policy on alarm management that covers these existing alerts - Clinical Alarm Management GPP-242 – link to policy below: <http://policies.mountsinai.org/web/general-policies-and-procedures/policies/-/policy-management/viewPolicy/565852/>.

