Description of the Source Records that Will Be Used to Collect Data About Subjects

For each patient, real-time data from the EHR, the admitting system (Cerner ADT), the ECG (MUSE), and laboratory information systems (SCC) will be ingested by the ReSCUE-ME engine and used to generate a prediction score. Additional information provided by the RRT team on the result of the RRT intervention will be extracted from REDCap. These values as specified in Appendix 3 will be processed through the ReSCUE-ME data streaming engine to generate a MEWS++ score for patients who have not been excluded or withdrawn from the study. If an individual withdraws participation from the study, all data pertaining to this patient's current visit will be removed from

ReSCUE-ME. Clinical documents may also be assessed for the purpose of further clarification of events during the RRT intervention.

Description of Data that Will Be Collected Including Long-Term Follow-Up

The data that will be collected during this study include vitals, electrocardiogram, laboratory data, clinical evaluations, and patient demographics from ADT, Epic, MUSE, and Laboratory Information System. A detailed list is provided in Appendix 3. At this time we do not plan on conducting long-term follow-up upon the discharge of the patient from their current hospital visit.

Research Requires HIV Testing No

12. Procedures - Genetic Testing

Genetic Testing Will Be Performed No

Guidance and Policies > Future Use Data Sharing and Genetic Research

13. Procedures - Details**Surveys or Interviews** Yes**Type of Instruments Being Used** Created By Research Team**Description of Instruments Created By Research Team**

A REDCap survey will be created to understand the impact of the alerts on the RRT team. This clinician survey has not yet been developed. We will not do this piece of the research until the survey has been approved by the IRB and the protocol modified appropriately and also approved.

Audio / Photo / Video Recording No**Deception** No**Results of the Study Will Be Shared** No
with Subjects or Others

14. Procedures - Instruments**Instruments Created By Research Team**

Type	REDCap RRT survey
Name	REDCap RRT survey
Upload	REDCap RRT Survey Placeholder.docx

15. Procedures - Compensation

Compensation for Participation No

16. Consent - Waiver of Informed Consent

Requesting Waiver For

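### Investigator withdrawal is open-ended, decided with the arm known, and stops outcome collection as well as alerts, so later outcomes can be lost unequally between arms

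*Combined protocol and SAP*

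**What the plan says.** Protocol Section 9 (Procedures for Investigator to Withdraw Subjects) gives the authority to one person: "The Principal Investigator may stop subject involvement in this research study at any time without subject consent". Besides closure of the study, the grounds are that "the instructions of the study team have not been followed, the investigator believes it is in their best interest, or for any other reason". The next paragraph says what not participating or withdrawing means: "the alerting will be suppressed/turned off for the patient, their data will not be collected, and no alerts will be sent". It then adds: "Any data or alerts prior to withdrawal will be retained".

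Section 11 (Description of the Source Records) says something different about an individual who withdraws: "all data pertaining to this patient's current visit will be removed from" ReSCUE-ME.

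Allocation is by hospital unit. Section 11 (Description of the Study Design) says of the control units: "Patients on 9W and 9E will be followed but no alerts, interventions or changes from standard of care will be pursued". No blinding is described.

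The Final Statistical Analysis Plan (December 2021, Patient Level Analysis) sets the treatment group by arm at admission. It models counts over the whole hospital stay, and in-hospital and 30-day death as binary outcomes. It has no rule for withdrawn patients, no censoring rule for them, and no report of withdrawals by arm or reason.

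**The concern.** Two separate acts, stopping the alerts and stopping outcome capture, are tied together in one discretionary decision. Whoever takes it knows the arm. The study team also has a running view of the alerts: Section 10 says "we will be continuously trending the alert burden of the study via the web dashboard and other custom analytic tools", and describes matching alerts to RRT visits. Only minimum safety monitoring applies (Section 20), under which the principal investigator is typically the monitor. No independent check on withdrawals is described.

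If the chance of withdrawal is related to the patient's risk of escalating and differs by arm, the lost follow-up is informative. Analysis by arm at admission does not repair this, because it cannot restore outcomes that were never collected. A patient who stays in the denominator with later events unrecorded counts as event-free. The rule covers all four units, but reasons connected with alerts are more likely to come up on 10E and 10W, where alerts are sent. The planned effect is small, so modest selective loss could matter for escalation, and the same mechanism applies to mortality.

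**Working it through.** **Inputs.** From the sample size calculation (Section 19): escalation rate about 10%; at least 50% of escalations identified; about 20% of those prevented; margin 5%; 934 escalations and 9,340 bed movements per group. From Section 3 (Background): alert precision 0.3 in the silent pilot and 0.12 in the retrospective cohort. The documents give no withdrawal rate.

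**The plan's own figures.**
- Expected effect: 10% × 50% × 20% = 1 percentage point, so 10% falls to 9%.
- Size: 934 / 0.10 = 9,340 per group; 2 × 9,340 = 18,680. These are exact, so there is no allowance for withdrawal.
- The 934 reproduces with rounded z values as a per-arm non-inferiority number: (0.09 + 0.09) × (1.96 + 1.64)² / 0.05² = 933.1, rounded up to 934. The plan uses it as a count of escalations. That is a separate matter; here I take 934 and 9,340 as the plan states them.

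**Model.** Assume no true effect, so the alert arm has 934 escalations in 9,340. Let w patients in that arm be withdrawn before any event, with escalation risk r.
- Truncated follow-up (Section 9): rate = (934 − r·w) / 9,340
- Removal of the visit (Section 11): rate = (934 − r·w) / (9,340 − w)

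**Worst case, r = 1** (every withdrawn patient would have escalated, all in the alert arm):

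| w | Share of arm | Truncated | Removed |
|---|---|---|---|
| 47 | 0.5% | 887/9,340 = 9.50% | 887/9,293 = 9.54% |
| 93 | 1.0% | 841/9,340 = 9.00% | 841/9,247 = 9.09% |

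With 5% of would-be escalators lost, a two-sided 5% comparison of two proportions at 9,340 per arm would favour alerts with probability about 21% (truncated) or 18% (removed). With 10% lost, the figures are 64% and 56%. There is no true effect in either case.

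**Softer case, r = 0.3** (assumption: pilot precision taken as the withdrawn patients' escalation risk). Solving for w:
- To reach 9.5%: truncated 46.7 / 0.3 = 156; removed 46.7 / (0.3 − 0.095) = 228. That is 1.7% to 2.4% of the arm.
- To reach 9.0%: truncated 93.4 / 0.3 = 311; removed 93.4 / (0.3 − 0.09) = 445. That is 3.3% to 4.8%.

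**Lower risk, r = 0.12** (assumption: retrospective precision). Reaching 9.0% takes 93.4 / 0.12 = 778 (truncated) or 93.4 / (0.12 − 0.09) = 3,113 (removed), which is 8.3% or 33% of the arm.

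**Direction.** If the withdrawn patients would not have escalated (r = 0, w = 93), truncation leaves 10.00% and removal gives 934/9,247 = 10.10%. Losses on the control units would push the comparison the other way.

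**The case against.** The best defence is the retention sentence: "Any data or alerts prior to withdrawal will be retained". A reader might infer that the investigator can delete patients, or erase an escalation already seen. Section 9 does not support that: a recorded event stays and only later follow-up is lost. Deletion could come only from Section 11, which is worded for an individual who withdraws. It speaks of removal from ReSCUE-ME, which names both the study and its data engine, so its effect on the analysis data is unclear.

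A reader might also infer that the ground about instructions can apply only in the alert arm, because "Patients admitted to 9W and 9E will not undergo any additional monitoring and thus will serve as controls", and that a comparable control patient could not be withdrawn. The documents do not say so. Section 9 states one rule for all four units, and the best-interest and any-other-reason grounds reach controls equally. The instructions are not defined, Section 16 gives staff on the participating units instructions about withdrawing patients, and Section 10 leaves the response to an alert to the provider. An alert that was not acted on is therefore not clearly a breach.

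Nor does truncation break the SAP's arm-at-admission rule: the patient keeps the arm and loses later outcomes.

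Alert burden also has its own route: a review committee (Section 10), a cap and refractory window (Section 11), and per-patient suppression described for opt-out. Nothing shows that withdrawal was used to handle troublesome alerts.

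All of this stands, and it limits the point to a potential bias. It does not remove it: the discretion has no limit, withdrawal ends outcome collection, and the SAP is silent on withdrawn patients.

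**Conclusion.** The point holds as a correctable weakness in design and reporting. An open-ended decision, taken with the arm known, ends outcome collection, while the SAP needs outcomes over the whole stay. Sections 9 and 11 disagree on what happens to data already collected and must be reconciled.

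The size is conditional. Under the worst-case assumption, 47 withdrawals could produce about half of the planned 1-point effect and 93 about all of it. At an assumed risk of 0.3 the corresponding numbers are 156 to 228 and 311 to 445; at lower risk they are much larger. All of these put every withdrawal in the alert arm before the event, and use bed movements, whereas the final SAP analyses first hospitalizations with weighting. Neither frequency nor direction is documented, so the documents do not show that the result was biased or that it was biased in favour of alerts.

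**What to change.** In Section 9, separate the two acts:
- Investigator-initiated withdrawal stops alerting only. The investigator's authority to suppress alerts is unchanged.
- Routine EHR outcome collection continues, and the patient is analysed in the arm at admission.
- Loss of later data is limited to opt-out by the patient or representative.
- Sections 9 and 11 state one rule for data collected before withdrawal.
- Date, arm and reason are logged for every withdrawal or suppression.
- The information sheet is aligned, since Section 9 says the present definition was added to the consent material.

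This is feasible: Section 11 says notifications can be suppressed per patient, and outcomes come from existing hospital systems.

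The protocol reports no changes during the study and the final SAP is in the past tense. If enrolment is complete, report investigator withdrawals by arm, reason and timing, recover routine outcomes where the waiver permits (its form is not among the documents seen), and add a sensitivity analysis for outcomes lost after withdrawal. If there were none, one sentence saying so closes the matter.

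The cost is a small log, a matching edit to the information sheet, and slight dilution of the effect from patients whose alerts were stopped.
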